### 2.2. Secondary objectives

To determine if bicalutamide + camostat:

- Decrease the proportion of people with symptoms at day 7 and day 21
- Are safe to give in outpatients with COVID-19
- Decrease all-cause mortality at 60 days

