### 2.5. Secondary endpoints

- Proportion of people with symptoms at day 7 and day 21

- Proportion of drug-related AEs and SAEs
- All-cause mortality at day 60

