## 4. Treatment Plan

### 4.1. Study design

This will be a randomized, open-label study to determine if camostat+ bicalutamide decreases the proportion of people with COVID-19 who require hospitalization, compared to historical controls. Patients with symptomatic COVID-19, diagnosed as outpatients, will be randomized 1:1 stratified by gender and receipt of SOC drugs/vaccine, to treatment with standard of care alone or with camostat+bicalutamide . The schema is shown below:

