### 7.2. Relationship

The relationship of an AE to the administration of the study drug is to be assessed by the investigator according to the following definitions:

- No (unrelated, not related, no relation): The time course between the administration of study drug and the occurrence or worsening of the adverse event rules out a causal relationship and another cause (concomitant drugs, therapies, complications, etc.) is suspected.
- Yes (related): The time course between the administration of study drug and the occurrence or worsening of the adverse event is consistent with a causal relationship and no other cause (concomitant drugs, therapies, complications, etc.) can be identified.

The following factors should also be considered:

- The temporal sequence from study drug administration - The event should occur after the study drug is given. The length of time from study drug exposure to event should be evaluated in the clinical context of the event.
- Underlying, concomitant, intercurrent diseases - Each report should be evaluated in the context of the natural history and course of the disease being treated and any other disease the subject may have.
- Concomitant medication - The other medications the subject is taking or the treatment the subject receives should be examined to determine whether any of them might be recognized to cause the event in question.
- Known response pattern for this class of study drug - Clinical and/or preclinical data may indicate whether a particular response is likely to be a class effect.
- Exposure to physical and/or mental stresses - The exposure to stress might induce adverse changes in the recipient and provide a logical and better explanation for the event.
- The pharmacology and pharmacokinetics of the study drug - The known pharmacologic properties (absorption, distribution, metabolism, and excretion) of the study drug should be considered.

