## 7.5. Reporting

Information about all adverse events, whether volunteered by the subject, discovered by investigator questioning, or detected through physical examination, laboratory test or other means, will be collected, recorded, and followed as appropriate.

All adverse events experienced by subjects will be collected and reported from the first dose of study drug, throughout the study, and will only be followed for 28 days unless related to the investigational agent.

Subjects who have an ongoing adverse event related to the study procedures and/or medication(s) may continue to be periodically contacted by a member of the study staff until the event is resolved or determined to be irreversible by the investigator.

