### 7.5.1. SAE Reporting

All SAEs (including deaths) occurring from the first dose of the study drug through 28 days after the last dose of study drug will be collected and recorded on the Adverse Event Case Report Form (CRF).

All SAEs should be reported to the IND Sponsor ([contact]) and Ono Pharmaceutical Co., Ltd ([contact]) within 24 hours of becoming aware of the event occurrence using the **SAE Reporting Form**. **Section 12.3** outlines reporting requirements for the DSMB.

SAEs will be reported to the Johns Hopkins Medicine IRB per institutional guidelines.

Adverse events that are serious, unexpected, and assessed by the investigator to be related to the study drug will be reported within 24 hours of becoming aware of the event occurrence to the post-marketing departments of the drug manufacturer.

After the initial SAE report, the investigator is required to proactively follow each subject and provide further information in regards to the subject's condition.

All AE(s) and SAE(s) will be followed until:

- Resolution
- The condition stabilizes
- The event is otherwise explained
- The subject is lost to follow-up
- Death

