### 11.2. Analysis of the secondary and exploratory endpoints

The proportion of people with symptoms will be compared to the proportion of people without symptoms and compared using chi-squared test. Proportions with drug-related adverse events and serious adverse events will be compared using chi-squared test. All-cause mortality at day 60 will be compared using Fisher's exact test and a time to event analysis using Kaplan-Meier methods will be used to compare the two arms.

Descriptive statistics will be used to summarize and compare the exploratory endpoints.

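### Sections 2.5 and 11.2 test drug-related adverse events against a control count that is zero by construction, and the AE and SAE windows lack control-arm dates

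*Combined protocol and SAP*

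**What the plan says.** Section 2.2 makes safety a secondary objective: whether the two drugs "Are safe to give in outpatients with COVID-19". Section 2.5 gives the matching endpoint as "Proportion of drug-related AEs and SAEs". Section 11.2 gives the analysis: "Proportions with drug-related adverse events and serious adverse events will be compared using chi-squared test". It names neither the groups compared nor a significance level.

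Section 4.1 describes the trial thus: "This will be a randomized, open-label study". Patients are randomized "to treatment with standard of care alone or with camostat+bicalutamide", with no placebo. On causality, section 7.2 says "The relationship of an AE to the administration of the study drug is to be assessed by the investigator".

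The collection rules are tied to dosing. Section 7.5: "All adverse events experienced by subjects will be collected and reported from the first dose of study drug", continuing for the duration of the study. Section 7.5.1 collects "All SAEs (including deaths) occurring from the first dose of the study drug through 28 days after the last dose of study drug".

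Other provisions cover both arms. Section 7.1.1 dates an AE from the start of study drug or therapy, whether or not it is related. Section 6.5 schedules toxicity calls in all arms on days 3, 7, 21 and 60. The AE row of the section 10 calendar is not limited to one arm.

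**The concern.** A patient who never takes a study drug cannot have an event related to it. For drug-related AEs the control arm therefore supplies no information, and the p-value is a function of one number: how many treated patients have an event that an unblinded investigator calls related.

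The control arm is what could separate drug effects from COVID-19. Section 8.2 lists nausea, vomiting, abdominal pain, fatigue and anorexia as possible signs of bicalutamide liver injury, and all five are also on the Appendix A symptom form. The error can run either way. Liberal attribution produces an apparent excess with no drug effect behind it. Strict attribution hides a real excess, because section 7.2 accepts an event as related only if no other cause can be identified, and every enrolled patient has symptomatic COVID-19.

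Section 11 says that the trial's safety results will inform a larger confirmatory study. As written, the AE component cannot show whether treated patients had more events than untreated ones.

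**Working it through.** The plan gives no figure for the safety comparison. Its only between-arm figure, 80% power for hospitalization (section 11), reproduces at 80.3% by full enumeration but does not bear on this point.

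**Inputs.** 20 patients per arm (sections 3, 4.1 and 11). Drug-related AE count in controls: 0 (sections 4.1 and 7.2). Test: chi-squared, with no continuity rule stated (section 11.2). My assumptions: the comparison is between arms, and the level is two-sided 0.05.

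**1. The test against a fixed zero.** Let x of 20 treated patients have a related event, against 0 of 20 controls.

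- Pearson: 40(20x)² / [20·20·x(40−x)] = 40x/(40−x)
- Yates: 40(20x−20)² / [20·20·x(40−x)] = 40(x−1)² / [x(40−x)]
- Fisher, two-sided: 2·C(20,x)/C(40,x)

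| x | Pearson statistic | Pearson p | Yates p | Fisher p |
|---|---|---|---|---|
| 3 | 120/37 = 3.24 | 0.072 | 0.230 | 0.231 |
| 4 | 160/36 = 4.44 | 0.035 | 0.114 | 0.106 |
| 5 | 200/35 = 5.71 | 0.017 | 0.056 | 0.047 |
| 6 | 240/34 = 7.06 | 0.008 | 0.027 | 0.020 |

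The test reduces to a cut-off on x: 4 (Pearson), 5 (Fisher) or 6 (Yates). The expected event count is x/2 per arm, below 5 until x = 10, so the chi-squared approximation is doubtful across this range.

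**2. Illustration with no drug effect.** Suppose the all-cause AE rate is b in both arms and a share f of treated-arm AEs is labelled related. Then x is Binomial(20, b·f). The documents give neither b nor f; both are assumptions.

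| b | f | b·f | Chance of x ≥ 4 (Pearson p<0.05) | Chance of x ≥ 6 (Yates p<0.05) |
|---|---|---|---|---|
| 20% | 25% | 5% | 1.6% | below 0.1% |
| 30% | 25% | 7.5% | 5.8% | 0.3% |
| 30% | 50% | 15% | 35% | 6.7% |
| 40% | 50% | 20% | 59% | 20% |
| 60% | 50% | 30% | 89% | 58% |

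Comparing all-cause AEs between arms instead gives an error rate of 4.3% to 5.3% (Pearson) or 1.7% to 2.1% (Yates) for b from 20% to 60%.

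**3. SAEs: two readings.** If the qualifier drug-related also governs SAEs, the same zero applies. If it does not, the control count is not zero by construction and only the window problem remains.

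**4. Windows for a control patient.**

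| Rule | Anchor | Control patient |
|---|---|---|
| AE start (7.5) | first dose | no date |
| AE end (7.5) | duration of the study | defined |
| SAE start (7.5.1) | first dose | no date |
| SAE end (7.5.1) | 28 days after last dose | no date |

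Section 7.5 also limits AE follow-up to 28 days unless the event is related to the agent, an exception that no control event can meet.

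**5. Length of a common window.** Section 6.2 allows up to 72 hours from randomization to the start of treatment. To cover the dose-based SAE window in every treated patient, a window dated from randomization needs 3 + 7 + 28 = 38 days.

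**The case against.** A reader might infer that the randomized safety comparison is empty altogether, or that no control-arm safety data will exist. The documents do not support that. Section 11.1 compares hospitalization or death between arms, and section 11.2 compares all-cause mortality at day 60; neither uses attribution. The calls and calendar entries cover both arms, and the AE definition in section 7.1.1 does not require relatedness. Symptoms, with severity, are recorded without restriction by arm.

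The SAE endpoint can fairly be read as all SAEs: section 7.1.2 sets no relatedness condition, and section 12.3 sends every SAE and death to the DSMB. On that reading there is no structural zero. The window is still undefined for controls, and admissions for COVID-19 progression are not SAEs.

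It is also tempting to say that four attributed events suffice for significance. That is true only of uncorrected Pearson, which section 11.2 does not specify.

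Finally, an all-cause comparison at this size is weak. For 20% against 40% its power is about 29%, and for 30% against 60% about 46% (uncorrected chi-squared). That limits what the corrected analysis can detect, but does not justify a comparison in which the control arm plays no part.

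These points narrow the concern. The zero for drug-related AEs and the missing control-arm dates stand.

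**Conclusion.** The point holds for drug-related AEs: the planned test is a threshold on an open-label attributed count, not a randomized comparison. For SAEs the plan must first say what it means; on either reading the collection window has no dates for control patients. The structural zero follows from the documents alone. The cut-off of 4, 5 or 6 of 20 rests on the assumed 0.05 level and on which version of the test is used. The false-positive figures, from under 1% to 89%, rest on assumed event rates and attribution shares and only illustrate how far attribution drives the result.

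The defect lies in endpoint and window wording, not in an absence of control data. It should be fixed, but it concerns a secondary endpoint and leaves the primary analysis and DSMB oversight untouched.

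**What to change.** - **Sections 2.5 and 11.2:** make the between-arm safety endpoints the proportions of patients with any AE, any grade 3 or higher AE and any SAE, regardless of relatedness, compared as randomized with Fisher's exact test. State that SAEs means all SAEs. Report drug-related events descriptively, in the experimental arm only.
- **Sections 7.1.1, 7.5 and 7.5.1:** define one analysis window from randomization, identical in both arms, ending no earlier than day 38 or at the scheduled day-60 contact. Keep the dose-based window for regulatory reporting.

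The day-60 end is simpler to run: no contact falls near day 38, so events between the day-21 and day-60 contacts would have to be dated from recall or records.

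The cost is wording, plus somewhat more AE recording in control patients. No new visits are needed. AE reporting stays open-label, so the change removes the dependence on attribution but not all reporting bias.

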## 3. Patient Selection

A total of 40 patients will be recruited.

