#### 6.2. Randomization

Once eligibility is confirmed, patients will be randomized to a treatment group in a 1:1 fashion and stratified by gender and by receipt of SOC drugs/vaccine. All patients must commence treatment within 72 hours of randomization.

Eligible patients will be entered on study centrally at the Sidney Kimmel Comprehensive Cancer Center at the Johns Hopkins University by the Lead Study Coordinator. All sites should call/email the coordinating center at [[contact]](mailto:[contact]) for registration. The Registration Form and Eligibility Worksheet will be supplied to each participating site.

Subjects who sign a consent form, but do not initiate protocol treatment for any reason (e.g., subjects who are screen failures), will be replaced and will not count towards our accrual goal. The Coordinating Center should be notified as soon as possible.

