## 11. Statistical considerations

Our null hypothesis is that 20% of patients will require hospitalization by day 28. This is based on internal data (from [name] EPIC analysis team at Johns Hopkins Hospital) that demonstrates an overall hospitalization rate of 14% and a hospitalization rate of 18-20% in patients 60 years old and older. We expect that each of the investigational treatment will reduce it to 2% or lower.

The sample size of 20 in each investigational arm is determined based on the comparison to the control arm. The design gives us 80% power to detect a decrease in hospitalization rate from 20% in the control arm to 2% in the treatment arm, based on a one-sided Fisher's exact test with type I error of 0.25.

If we observe 1 or less patient hospitalized within 28 days since randomization in an investigational arm, we reject the null rate of 20% in favor of 4% or less hospitalization rate with that treatment. **Table 1** lists the 90% confidence intervals for various scenarios of observed proportion of hospitalized patients. **Table 2** shows the probability of observing 1 or less hospitalized patient under various true rates. If the true rate is 20% in Arm B or Arm C, the chance of observing only 1 or less hospitalization is low at 7%; and that chance is greater than 80% if the true hospitalization rate is 4% or lower. Given this is a small study, and the true effect size is unknown, the estimates and safety generated in this trial will be used to inform power calculations of a larger, confirmatory trial.

**Table 1.** Confidence intervals for various observed proportions of hospitalized patients in each arm.

Observed # of hospitalizations (out of 20)	Observed hospitalization rate	90% CI (Wilson method)
0	0%	[0, 11.9%]
1	5%	[1.1%, 19.6%]
2	10%	[3.4%, 26.2%]
3	15%	[6.2%, 32.2%]
4	20%	[9.3%, 37.8%]
5	25%	[12.7%, 43.2%]
6	30%	[16.4%, 48.4%]
7	35%	[20.2%, 53.3%]
8	40%	[24.2%, 58.1%]

**Table 2.** True hospitalization rate and probability of observing 1 or less hospitalization for each arm.

True hospitalization rate	Probability of observing 1 or less hospitalization (out of 20 patients)
1%	98%
2%	94%
3%	88%
4%	81%
5%	74%
6%	66%
10%	39%
15%	18%
20%	7%
25%	2%

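### The safety objective is analysed only by a chi-squared test of difference at 20 per arm, with no interval for either arm or for the excess, so a non-significant result could not support a statement of safety

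*Combined protocol and SAP*

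**What the plan says.** Section 2.2 lists among the secondary objectives to determine whether bicalutamide plus camostat "Are safe to give in outpatients with COVID-19". Section 2.5 gives the matching endpoint: "Proportion of drug-related AEs and SAEs". Section 11.2 gives its analysis in one sentence: "Proportions with drug-related adverse events and serious adverse events will be compared using chi-squared test". That sentence states no interval, margin, significance level or sidedness.

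On size, section 3 says "A total of 40 patients will be recruited", section 6.2 says "patients will be randomized to a treatment group in a 1:1 fashion", and section 11 says "The sample size of 20 in each investigational arm is determined based on the comparison to the control arm". That makes 20 per arm. The only type I error in the documents belongs to the hospitalization comparison, "based on a one-sided Fisher's exact test with type I error of 0.25".

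Estimation is planned for hospitalization: Table 1 in section 11 gives 90% Wilson intervals for outcomes out of 20, and 11.1 adds a 95% interval per arm for hospitalization or death. On later use of the results, section 11 says "the estimates and safety generated in this trial will be used to inform power calculations of a larger, confirmatory trial".

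**The concern.** A test of difference can contribute to a claim of safety only by failing to reject, and with 20 per arm it fails to reject for most excesses a reader would care about. The objective asks how large the harm could be; the analysis returns a p-value that does not say. What is missing is the pair of quantities that would answer the objective: the event rate in each arm with its uncertainty, and the range of between-arm excess compatible with the data.

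At stake is how the secondary safety result is reported and what reaches the confirmatory trial. Planning that trial needs rates with bounds. The plan already gives these for hospitalization but not for adverse events.

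**Working it through.** **Inputs.** From the documents: 20 per arm (sections 3, 6.2 and 11), the chi-squared test (11.2), the 90% Wilson intervals (section 11, Table 1) and the 95% level (11.1). Assumed, because the documents do not give them: event rates, test level, and whether a continuity correction is used.

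**1. The plan's own figures.** Enumerating all 21 × 21 outcomes for two binomials of size 20, with rejection when the one-sided Fisher p-value is at most 0.25, gives power 0.803 for 20% v 2%. This agrees with the stated 80%. For zero events the Wilson upper limit is z²/(n + z²). At 90% this is 2.706/22.706 = 11.9%, as in Table 1. At 95% it is 3.841/23.841 = 16.1%.

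**2. What the chi-squared test can detect.** With t treated and c control events, N = 40 and s = t + c, Pearson's statistic is X² = N(t − c)²/[s(N − s)], and it rejects at two-sided 0.05 when X² > 3.841.
- 3 v 0: 40·9/(3·37) = 3.243, p = 0.072.
- 5 v 1: 40·16/(6·34) = 3.137, p = 0.077.
- 6 v 1: 40·25/(7·33) = 4.329, p = 0.037. With one control event, six treated events are needed.

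Summing binomial probabilities over the non-rejecting outcomes gives the chance of missing an excess (control v treated, uncorrected, two-sided 0.05):
- Fourfold rises: 1% v 4%, 99.4%; 2.5% v 10%, 91.6%; 5% v 20%, 70.8%; 7.5% v 30%, 53.7%; 10% v 40%, 37.7%.
- Other contrasts: 5% v 15%, 84.7%; 10% v 20%, 86.4%; 10% v 30%, 64.3%.

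For 5% v 20% under other choices: continuity correction, 89.5%; two-sided Fisher, 83.2%; two-sided 0.10, 55.7%; one-sided 0.25, 21.0%.

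The expected count per arm is 20p, which is below 5 for any rate under 25%. With both true rates at 5%, the nominal 5% test rejects only about 1.2% of the time. Sections 11.1 and 11.2 use Fisher's test for other endpoints.

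**3. What an interval would report.** With d = p_T − p_C and Wilson limits (l, u) for each arm, the Newcombe limits are d − √[(p_T − l_T)² + (u_C − p_C)²] and d + √[(u_T − p_T)² + (p_C − l_C)²]. At 95%, treated v control:
- 0 v 0: upper limit √(0.161²) = 16.1 points (11.9 at 90%).
- 1 v 0: −11.6 to 23.6 points.
- 3 v 0: 0.15 − √(0.098² + 0.161²) = −3.8 points, and 0.15 + 0.210 = 36.0 points.
- 5 v 1: 0.20 − √(0.138² + 0.186²) = −3.2 points, and 0.20 + √(0.219² + 0.041²) = 42.3 points.

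**4. Keeping the level consistent.** At 90% the intervals for 3 v 0 (0.2 to 32.2) and 5 v 1 (0.9 to 38.6) exclude zero, but at the matching two-sided 0.10 the test rejects in both cases as well. At 95% both intervals include zero, and the test at 0.05 does not reject. In these examples test and interval agree once the level is the same. What the interval adds is the upper limit.

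**The case against.** **A decision rule that is not there.** A reader might infer that a non-significant result will be reported as showing the combination to be safe. No section says so. Section 11 calls this a small study and carries estimates and safety forward to a larger trial, and the endpoint in 2.5 is itself a proportion. This objection stands. The defect is that the planned analysis cannot answer the stated objective, not that the plan commits to a false conclusion.

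**A single miss rate.** It is tempting to say that a fourfold rise in serious events is missed 71% of the time. That figure needs 5% v 20%, two-sided 0.05 and no continuity correction, none of which is in the documents. If drug-related in 2.5 covers serious events as well, controls could have a rate near zero; at 0% v 20% the same test misses 41%, and 4 v 0 gives p = 0.035. This also stands, so the figures serve only as a range.

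**Harm that the interval would flag and the test would miss.** Comparing 90% intervals with a test at 0.05 gives that impression. It comes from mixing levels and should not be claimed.

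**Other safety oversight.** A DSMB receives every SAE and death, meets after the first 10 patients per treatment arm and every three months (12.3). There are safety meetings, weekly or as needed (12.2), and a day-60 mortality comparison (11.2). Safety judgement therefore does not rest on one p-value. But none of these bounds an adverse event rate, and 12.3 sets no numerical criterion.

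**No margin in the remedy.** Intervals alone still do not define what counts as safe. That is correct, and it is why the objective in 2.2 should be reworded along with 11.2.

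**Conclusion.** The point holds as a mismatch between objective and analysis. Section 2.2 asks whether the combination is safe to give; 11.2 offers only a difference test on 20 per arm, with no interval for either proportion or for their difference. A non-significant result from that test cannot support a statement of safety. This conclusion does not depend on the assumed rates.

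The size does depend on them. Under the uncorrected two-sided 0.05 test, 5% v 20% is missed about 71% of the time, and fourfold rises from about 99% (1% v 4%) to 38% (10% v 40%). At one-sided 0.25, a level the documents set for hospitalization and not for safety, 5% v 20% is missed 21%.

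This is a cheap improvement to a secondary objective. It leaves the primary analysis untouched.

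**What to change.** In 11.2, replace the chi-squared sentence for safety with wording such as:

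> The proportion of patients with AEs and with SAEs will be reported for each arm with a 95% Wilson interval, and the between-arm risk difference with a 95% Newcombe interval. The upper limit will be reported as the largest excess not excluded. Absence of statistical significance will not be taken as evidence of safety.

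Use 95% throughout, to match 11.1. In 2.2, reword the safety objective as estimating the incidence of AEs and SAEs and the excess compatible with the data.

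The change needs no new data, patients or visits. Wilson intervals are already in Table 1; the Newcombe interval would be new to the plan but is built from the same Wilson limits. The downside is a less favourable safety statement, since even no events in either arm leaves an excess of up to about 16 points unexcluded at 95% (12 points at 90%).
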